2.5.4 Safety Analysis

Differences in the occurrence of adverse events between groups will be assessed with chi-square tests with a significance level p < 0.05. Descriptive statistics will be used to report occurrence of adverse events in the pilot group.

3.0 Risk Analysis

3.1 Anticipated Risks

To mitigate risk to patient confidentiality, data will be kept in encrypted files on a secure UPMC server. The identifying patient information will be kept in a second document separate from the clinical data gathered, and a non-identifying code will be assigned to each patient. The data collected will not be shared with any person(s) not included in the study investigator list. Should a breach of conduct occur, the IRB will be notified immediately by one of the principal investigators.

Participants in the intervention arm will undergo an invasive procedure and will be subjected to moderateto-high risk. Risks include but are not limited to bleeding at the puncture site, infection, damage to nearby structures, synovitis, worsening of groin hematoma, and nontarget embolization. A qualified, boardcertified interventional radiologist will perform the procedure. Sterile technique will always be followed. Radiation exposure to the patient will be minimized using standard strategies (e.g. aggressive collimation, minimizing fluoroscopy time). All adverse events will be thoroughly documented and reported to the UPMC IRB immediately.

Because the study population has osteoarthritis-related knee symptoms refractory to conservative management, the next treatment option traditionally available is knee replacement surgery. Transarterial embolization, while still an invasive procedure, has a much lower risk profile that knee replacement surgery.

This trial will include 15 initial patients to confirm safety and initial efficacy of the treatment. Patients will include both male and female and range from age 18-75 who meet the inclusion criteria as detailed above. GAE will be performed by the trained investigating Interventional Radiologists who have significant experience in performing endovascular embolization procedures.

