Study Title: Geniculate Artery Embolization for the Treatment of Knee Osteoarthritis 04/08/2025

G190248 Supplement 001

A. Cover Page

Device Information : Device name: Teleflex Gel-Bead

Intended use of device:

The Gel-Bead embolization particles will be used to perform geniculate artery embolization (GAE) for the purposes of treatment of osteoarthritis-related knee pain.

Device Information:

Device name: Teleflex Gel-Bead

Intended use of device:

The Gel-Bead embolization particles will be used to perform geniculate artery embolization (GAE) for the purposes of treatment of osteoarthritis-related knee pain.

Sponsor-Investigator and Correspondent Contact Information:

[name] University of Pittsburgh Medical Center [name] [contact] / [contact] [contact]

Manufacturer Information:

Teleflex (acquired Vascular Solutions, Inc. February 2017) [name] [contact]

Distributed by Medtronic

Referenced files: There are no referenced files.

Protocol Ammendments:

Updated protocol to remove 6-minute walk test due to feasibility issues in performing

B. Clinical Plan

The primary goal of our investigation is to determine if geniculate artery embolization (GAE) will result in a decrease in pain and disability caused by knee osteoarthritis. The investigation will be conducted as two distinct studies:

 A pilot study of GAE for the treatment of knee osteoarthritis
 A series of up to 30 subjects undergoing geniculate artery embolization will be included in this arm with the explicit purpose to demonstrate safety and efficacy.

The primary endpoint of this study is overall efficacy of treatment as determined by a minimal clinically significant improvement in KOOS pain score of 10 based on the KOOS Pain questionnaire at 6 months.

Secondary outcomes will be improvement in functionality and quality of life based on the KOOS Function in Sport and Recreation, and KOOS Quality of Life Scales. Secondary outcomes will also include changes in quantitative functional metrics as well as reduction in medication use.

Technical success will be defined as the performance of diagnostic angiography of the knee with delivery of the Gel-Bead particles to a region of hypervascularity within the knee resulting in reduced flow/occlusion of the target vessels. Clinical success will be defined by a decrease in pain of 10 points per the KOOS questionnaire at 6 months.

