1.0 Purpose of the Investigation

Osteoarthritis is an increasingly prevalent disease and often results in functionally limiting joint pain. In 2015, an estimated 54 million adults (22.7%) in the United States had doctor-diagnosed arthritis, with 43.5% of those patients reporting lifestyle and activity limitations (1).

The knee is a commonly affected joint and results in an annual healthcare expenditure of \$27 billion (2). Definitive therapy for knee osteoarthritis is total knee arthroplasty. An estimated 54% of patients with knee osteoarthritis require a total knee arthroplasty within their lifetime, and 658,000 people undergo surgery annually (2-3). The goal of conservative management is to delay or eliminate the need for a total knee arthroplasty in patients. Currently, patients manage their pain with conservative management for an average of 13 years (2).

First line conservative management is treatment with physical therapy, weight loss, non-steroidal antiinflammatory medications, and corticosteroid injections. Opiate medications are being prescribed with increasing frequency, despite evidence that they do not effectively treat osteoarthritis pain (4).

Early trials have shown transcatheter embolization of abnormal neovasculature with microparticles can be effective in the treatment of mild to moderate knee osteoarthritis refractory to conservative management in select cases (5). This therapy aims to treat the angiogenesis and inflammatory component involved in the pathophysiology of osteoarthritis (6-7).

Thickening and hypertrophy of the knee synovium has a similar appearance on angiography to hypervascular tumors. Transcatheter arterial embolization with permanent and resorbable particles has been shown to be safe in early trials for treatment of knee osteoarthritis as well as in patients being treated for hemarthrosis, with small trials showing no major complications and 8-20% having minor self-resolving skin or puncture site complications (5, 8-9). Additionally, complications do not increase with repeat embolizations (9). The use of resorbable particles has a theoretical advantage as the particles will not permanently reside within tissue.

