2.2.1 General Study Design

A series of 15 patients undergoing geniculate artery embolization will be included in this arm with the explicit purpose to demonstrate safety and efficacy.

This trial will assess reduction in pain, functional improvement, and reduction of conservative medical therapy in patients with mild to moderate knee osteoarthritis who have failed conservative

management, for 6 months and for up to two years following embolization.

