2.3.1 General characteristics of the proposed subject population

Similar to prior studies conducted on GAE, subjects included in the study will be those with mild to moderate knee osteoarthritis with moderate to severe pain that is refractory to conservative management. These are patients who have significant symptoms but are not ideal candidates for total knee replacement.

2.3.2 *Anticipated number of research subjects*

For the Pilot Study, 30 patients are expected to enroll (defined as completion of the informed consent process as per University IRB policies) and all are expected to complete the study.

2.3.3 Inclusion Criteria:

1. Patients between ages 18 and 75 with moderate/severe knee pain secondary to primary osteoarthritis. Moderate/severe pain will be defined as pain 30 mm to

100 mm on the Visual Analog Pain Scale (where 0 denotes 'no pain' and 100 mm denotes worst pain imaginable')

- 2. Grade 1, 2, or 3 osteoarthritis on the Kellgren-Lawrence grading scale on knee x-ray in the last 12 months
- 3. Pain must be refractory to 3 months of medical management (which may include a combination of oral analgesics, intraarticular steroids, viscosupplementation, opioid therapy, etc)
- 4. Patients willing and able to consent to the study

2.3.4 Exclusion Criteria:

- 1 Kidney dysfunction defined as an estimated GFR < 60 mL/min
- 2 Acute knee injury
- 3 Current local infection
- 4 Prior ipsilateral knee replacement surgery
- 5 Infectious or inflammatory arthritis
- 6 History of contrast allergy resulting in anaphylaxis
- 7 INR (International Normalization Ratio) > 1.6
- 8 Platelets < 50,000
- 9 Significant atherosclerosis that would limit angiography
- 10 Active malignancy
- 11 Active pregnancy
- 12 Appropriate candidate for knee replacement surgery determined by clinical and physical examination
- 13 Recent within 3 months, or active cigarette user
- 14 Any other condition that in the opinion of the investigator would preclude the patient from participation.

2.4 Study Procedures:

2.4.1 Patient Recruitment:

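### The protocol promises to demonstrate or confirm safety, but it sets no criterion, plans no interval, relies on a between-group test with no second group described, and has too few patients at either stated N

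*Combined protocol and SAP*

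**What the plan says.** **The aim.** Section 3.1 (Anticipated Risks) says: "This trial will include 15 initial patients to confirm safety and initial efficacy of the treatment". Section 2.2.1 gives the series the "explicit purpose to demonstrate safety and efficacy", and the Clinical Plan in section B uses the same phrase.

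**The analysis.** Section 2.5.4 has two sentences. The first reads: "Differences in the occurrence of adverse events between groups will be assessed with chi-square tests with a significance level p < 0.05". The second reads: "Descriptive statistics will be used to report occurrence of adverse events in the pilot group". The endpoint sections (2.5.1.1 and 2.5.1.2) list pain, function, quality of life and medication use. They list no safety endpoint.

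**The number of patients.** Section 2.2.1 says: "A series of 15 patients undergoing geniculate artery embolization will be included in this arm". Sections 2.5.2 and 3.1 also use 15. The Clinical Plan says: "A series of up to 30 subjects undergoing geniculate artery embolization will be included in this arm". Section 2.3.2 says: "For the Pilot Study, 30 patients are expected to enroll".

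**The background.** Section 1.0 describes earlier work on embolization as "small trials showing no major complications and 8-20% having minor self-resolving skin or puncture site complications".

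**The concern.** To confirm or demonstrate safety, a plan needs three things: a defined event, a rate that would count as acceptable, and enough patients to exclude rates above it. The plan has none of them. Its one inferential tool is a comparison between groups, but the visit schedule in section 2.4 takes every subject through the same GAE procedure, so on the text available there is nothing to compare. What remains is descriptive reporting with no event, denominator or interval named.

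Section 3.1 itself rates the risk of the procedure as moderate to high, so how precisely complication rates are known bears on any decision to go further. Without an interval, a low or zero count gives no indication of how high the true rate could still be. The two values of N make this worse, because the precision differs by nearly a factor of two between them.

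**Working it through.** **Plan's own figure.** There is none to reproduce. The documents give no target complication rate, margin, bound or detection probability for safety. (The 22% in section 2.5.2 is a power figure for the KOOS Pain comparison. It is unrelated to the 21.8% below.)

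**Inputs.**
- n = 15 (2.2.1, 2.5.2, 3.1) or n = 30 (Clinical Plan as a maximum; 2.3.2 as the expected number). Section 2.3.2 expects all enrolled patients to complete, so no loss is applied.
- Confidence level 95%, exact binomial. This is an assumption, since the plan names no interval. Two-sided and one-sided limits are both shown.
- Illustrative true rates of 5% and 10%. These are also assumptions; the documents name no rate to be excluded.

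**Step 1: upper limit when no event is seen.** The exact limit solves (1 − p)^n = tail probability, so p = 1 − 0.025^(1/n) two-sided and p = 1 − 0.05^(1/n) one-sided.
- n = 15, two-sided: 1 − 0.025^(1/15) = 21.8%. One-sided: 1 − 0.05^(1/15) = 18.1%.
- n = 30, two-sided: 1 − 0.025^(1/30) = 11.6%. One-sided: 1 − 0.05^(1/30) = 9.5%.
- Cross-checks: the Wilson limits are 20.4% and 11.4%; the rule of three gives 3/15 = 20% and 3/30 = 10%.

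**Step 2: chance of seeing no event at a given true rate**, (1 − p)^n.

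| True rate | n = 15 | n = 30 |
|---|---|---|
| 5% | 0.95^15 = 46% | 0.95^30 = 21% |
| 10% | 0.90^15 = 21% | 0.90^30 = 4% |

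**Step 3: a non-zero count.** If 20% of patients had an event, the exact two-sided 95% interval would be 4.3% to 48.1% for 3/15 and 7.7% to 38.6% for 6/30.

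**Step 4: size needed for a tighter bound.** For the zero-event limit to be 10% or lower, n must be at least ln(0.025)/ln(0.90), which rounds up to 36 (two-sided), or ln(0.05)/ln(0.90), which rounds up to 29 (one-sided). The 10% is only an illustration.

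**Step 5: who is counted.** Section 2.4.2.1 withdraws subjects when a major complication prevents GAE from being performed or completed, and when they cannot complete at least one follow-up visit. Section 3.3 says that subjects will not be withdrawn because of adverse effects. These passages need reconciling. As no safety population is defined, patients with a bad procedural outcome could be left out of the denominator. Major and minor complications are mentioned in the procedure and withdrawal text, but the definitions in section 3.2.1 cover neither term.

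**The case against.** Several points on the other side stand.

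- **Descriptive reporting is planned and is ordinary for a pilot.** The second sentence of 2.5.4 gives the pilot group its own analysis. The gap is the missing interval, event and denominator, not the absence of any analysis. A reader could compute an exact interval from published counts, but only if event and denominator are clear.
- **The chi-square sentence may be left over from a comparative study.** The Clinical Plan announces two studies and describes one, 2.5.1.1 mentions a sham group, and the design figure is not available here. So one can say only that no second group is described in the available text, not that none was ever intended. A test that cannot be run also cannot yield a false result; it simply does nothing for the safety aim.
- **N may be 30.** The word initial in 3.1 could mean a first stage. At 30 the zero-event limit is about half that at 15, so both figures must be given.
- **Safety conduct is covered.** Recording, causality review, reporting and monthly team meetings are specified. They protect patients but do not add precision to a rate.

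A reader might infer that zero events in 15 patients would be declared safe under the plan. The documents do not support this, since no rule links an event count to a safety conclusion. Nor are the rates in section 1.0 a planned benchmark: they are background from small trials that mixed osteoarthritis with hemarthrosis patients and permanent with resorbable particles.

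**Conclusion.** The point holds. The plan states a property, confirmation of safety, that neither 15 nor 30 patients can deliver, and its only inferential safety analysis does not apply to the single treated group described. With no events seen, true rates up to 21.8% (n = 15) or 11.6% (n = 30) remain compatible with the data at the two-sided exact 95% level; the one-sided limits are 18.1% and 9.5%. An event with a true rate of 5% would be missed entirely with probability 46% or 21%. These figures assume independent patients, complete ascertainment and a 95% level that the plan does not itself name. The conclusion is unchanged under either sidedness and either N.

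The criticism is that the safety claim lacks a criterion and a precision statement. It does not extend to predicting how the investigators would interpret a particular count. The change should be made: it costs little and alters what the trial can say about safety.

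**What to change.** 1. Reconcile N across the Clinical Plan, 2.2.1, 2.3.2, 2.5.2 and 3.1.
2. In 2.5.4, delete the between-group chi-square test for this single-arm pilot.
3. In its place, specify the number and proportion of patients with at least one serious adverse effect, and with at least one device- or procedure-associated adverse effect, each with an exact (Clopper-Pearson) 95% confidence interval.
4. Define the denominator as all patients with arterial access for GAE, including any withdrawn under 2.4.2.1, and reconcile that section with 3.3.
5. Define major and minor complication before counting them; then report them in the same way.
6. In the Clinical Plan, 2.2.1 and 3.1, replace the language of demonstrating or confirming safety with estimating adverse-effect rates. State in advance the zero-event upper limit for the reconciled N: 21.8% if 15, 11.6% if 30 (two-sided 95%).
7. Cite the rates in section 1.0 as context only, because they come from different populations and embolics.

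The cost is protocol and analysis wording, with no added patients or visits. The downside is that the stated safety claim becomes less favourable.

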3.2 Adverse Event Recording/Reporting

3.2.1 Adverse Event Definitions

Adverse effect. Any untoward medical occurrence in a clinical study of an investigational device; regardless of the causal relationship of the problem with the device or, if applicable, other study treatment or diagnostic product(s).

Associated with the investigational device or, if applicable, other study treatment or diagnostic product(s). There is a reasonable possibility that the adverse effect may have been caused by the investigational device or, if applicable, the other study treatment or diagnostic product(s).

Disability. A substantial disruption of a person's ability to conduct normal life functions.

Life-threatening adverse effect. Any adverse effect that places the subject, in the view of the investigatorsponsor, at immediate risk of death from the effect as it occurred (i.e., does not include an adverse effect that, had it actually occurred in a more severe form, might have caused death).

Serious adverse effect. Any adverse effect that results in any of the following outcomes: death, a lifethreatening adverse effect, inpatient hospitalization or prolongation of existing hospitalization, a persistent or significant disability/incapacity, or a congenital anomaly/birth defect.

Hospitalization shall include any initial admission (even if less than 24 hours) to a healthcare facility as a result of a precipitating clinical adverse effect; to include transfer within the hospital to an intensive care unit. Hospitalization or prolongation of hospitalization in the absence of a precipitating, clinical adverse effect (e.g., for a preexisting condition not associated with a new adverse effect or with a worsening of the preexisting condition; admission for a protocol-specified procedure) is not, in itself, a serious adverse effect.

Unexpected adverse effect. Any adverse effect, the frequency, specificity or severity of which is not consistent with the risk information described in the clinical protocol(s) or elsewhere in the current IDE application, as amended.

Unanticipated adverse device effect. Any serious adverse effect on health or safety or any life- threatening problem or death caused by, or associated with, a device, if that effect, problem, or death was not previously identified in nature, severity, or degree of incidence in the investigational plan or IDE application (including a supplementary plan or application), or any other unanticipated serious problem associated with a device that relates to the rights, safety, or welfare of subjects.

3.2.2 Eliciting Adverse Effect Information

Clinical subjects will be routinely questioned about adverse effects at study visits.

3.2.3 Recording and Assessment of Adverse Effects

All observed or volunteered adverse effects (serious or non-serious) and abnormal test findings, regardless of treatment group or suspected causal relationship to the investigational device or, if

applicable, other study treatment or diagnostic product(s) will be recorded in the subjects' case histories. For all adverse effects, sufficient information will be pursued and/or obtained so as to permit 1) an adequate determination of the outcome of the effect (i.e., whether the effect should be classified as a serious adverse effect) and; 2) an assessment of the casual relationship between the adverse effect and the investigational device or, if applicable, other study treatment or diagnostic product(s).

Adverse effects or abnormal test findings felt to be associated with the investigational device or other study treatment or diagnostic product(s) will be followed until the effect (or its sequelae) or the abnormal test finding resolves or stabilizes at a level acceptable to the investigator-sponsor.

3.2.3.1 Abnormal Test Findings

An abnormal test finding will be classified as an adverse effect if one or more of the following criteria are met:

- The test finding is accompanied by clinical symptoms.
- The test finding necessitates additional diagnostic evaluation(s) or medical/surgical intervention; including significant additional concomitant drug or other therapy. (Note: simply repeating a test finding, in the absence of any of the other listed criteria, does not constitute an adverse effect.)
- The test finding leads to a change in study dosing or exposure or discontinuation of subject participation in the clinical study.
- The test finding is considered an adverse effect by the investigator-sponsor.

3.2.3.2 Causality and Severity Assessment

The investigator-sponsor will promptly review documented adverse effects and abnormal test findings to determine 1) if the abnormal test finding should be classified as an adverse effect; 2) if there is a reasonable possibility that the adverse effect was caused by the investigational device or, if applicable, other study treatment or diagnostic product(s); and 3) if the adverse effect meets the criteria for a serious adverse effect.

If the investigator-sponsor's final determination of causality is "unknown and of questionable relationship to the investigational device or, if applicable, other study treatment or diagnostic product(s)", the adverse effect will be classified as associated with the use of the investigational device or study treatment or diagnostic drug product(s) for reporting purposes. If the investigator-sponsor's final determination of causality is "unknown but not related to the investigational device or, if applicable, other study treatment or diagnostic product(s)", this determination and the rationale for the determination will be documented in the respective subject's case history.

3.2.4 Reporting of Adverse Effects to the FDA

The investigator-sponsor will submit a completed FDA Form 3500A to the FDA's Center for Devices and Radiological Health for any observed or volunteered adverse effect that is determined to be an unanticipated adverse device effect. A copy of this completed form will be provided to all participating sub-investigators.

The completed FDA Form 3500Awill be submitted to the FDA as soon as possible and, in no event, later than 10 working days after the investigator-sponsor first receives notice of the adverse effect.

If the results of the sponsor-investigator's follow-up evaluation show that an adverse effect that was initially determined to not constitute an unanticipated adverse device effect does, in fact, meet the requirements for reporting; the investigator-sponsor will submit a completed FDA Form 3500Aas soon as possible, but in no event later than 10 working days, after the determination was made.

For each submitted FDA Form 3500A, the sponsor-investigator will identify all previously submitted

reports that that addressed a similar adverse effect experience and will provide an analysis of the significance of newly reported adverse effect in light of the previous, similar report(s).

Subsequent to the initial submission of a completed FDA Form 3500A, the investigator-sponsor will submit additional information concerning the reported adverse effect as requested by the FDA.

